Anakinra, recombinant human IL-1 receptor antagonist (Kineret™, Biovitrum, Sweden) is approved in USA and Europe for the treatment of rheumatoid arthritis ⁷, and is also highly effective in the treatment of several inflammatory disease, and preliminary studies show benefits also in ischemic and hemorrhagic stroke and diabetes. The favorable safety profile of anakinra is witnessed by the hundreds of thousands of patients who have been treated in the past decades. Anakinra is associated with injection site reactions that are generally mild but occasionally severe. Also, anakinra is associated with an increased risk of infections (mainly upper respiratory infections) but it is not associated with an increased infection-related mortality showing that the infections occurring while on anakinra treatment are generally mild. Moreover, anakinra has been also tested in patients with severe sepsis and shock, and while it did not significantly reduce sepsis-related mortality, in a meta-analysis of all studies showed a favorable trend toward reduced mortality (-18%, P=0.08).

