5.2 Secondary Exploratory Endpoints

Additional endpoints will include parameters measured at echocardiography, as well as biomarkers, and clinical outcomes.

Echocardiography: structural and functional echocardiographic parameters include left and right ventricular dimensions, mass, systolic and diastolic function. These will provide mechanistic insight as to whether the hypothesized changes in the acute inflammatory response will correlate with changes in cardiac dimensions or function. The echocardiogram will be ordered acutely (within 24 hours) and at 1-year follow up as clinically indicated.

Biomarkers: Blood will be collected at each time-point throughout the study (admission, 72 hours [or discharge whichever comes first], 2 weeks, 3, 6 and 12 months) and analyzed for complete blood cell count, metabolic markers (including lipids and lipoproteins, glycemic control and insulin resistance, liver and renal panel, sterols), inflammatory markers (i.e. high sensitivity CRP) and cardiac biomarkers (i.e. NT-proBNP and troponin I). The data will be collected and electronically stored for further analysis at the conclusion of the study. When feasible, results from clinically indicated studies will be used.

Clinical outcomes: Incidence of death (cardiac and non-cardiac), hospitalizations (for HF, for other cardiac causes not related to HF, or for non-cardiac reasons) will be recorded at each time-point throughout the study (discharge, 2 weeks, 3, 6 and 12 months) in every patient, and then once at the end of study, by review of chart and/or telephone interview. The investigators and clinicians caring for the patients will remain blinded to treatment allocation and to the CRP data. Adjudication of events will be performed by an *ad hoc* committee blinded to treatment allocation and to CRP data.

6) ENROLLMENT IN THE STUDY

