7.1 Treatment with Anakinra

Anakinra and matching placebo syringes have already been provided by the manufacturer, Swedish Orphan Biovitrum (SOBI, Stockholm, Sweden) to the Investigational Pharmacy at the coordinating center at VCU, where the syringes are stored until ready to be administered to the patient. SOBI has also guaranteed a continuous supply of anakinra and placebo should the current supply expire prior to completion of the trial.

Patients will receive the first dose of anakinra 100 mg or placebo within 12 hours of coronary angiography/angioplasty. The drug will be administered by the nurse and the patients and will be instructed by one of the physicians or pharmacists in the team on how to store and self-administer the drug so they can continue at home twice daily for 14 days. The syringes will be labeled 1 through 28, the patient will be instructed to store them in the fridge and keep them at room temperature for few minutes prior to injection subcutaneously. Proper injection technique will be

taught. A sharp container sufficient to contain all 14 syringes will be given to the patient to dispose the syringes in, and to bring back at the 14-day visit.

One group of patients will receive anakinra 100 mg twice daily for 14 days, a second group will receive anakinra 100 mg alternated with placebo twice daily for 14 days so that anakinra will be given every 24 hours, the third group will receive placebo twice daily for 14 days. The patient will also be educated on expected side effects and need to inform the investigators about any foreseen and unforeseen events.

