8.1 Specification of Safety Parameters

Safety parameters will include data deriving from history and physical examination performed at each visit, laboratory data and results of functional and imaging tests. To enhance detection of adverse events between visits, all patients will be encouraged to contact the research team at any time with concerns or any perceived changes in their healthcare status.

Disease-related data (MI- and HF-related) will be assessed including changes in symptoms (or new symptoms), functional capacity, vital signs (including weight), renal function, or any significant changes in medications.

Data specific to the treatment will also be assessed. The patient will be asked about symptoms and examined for signs of infection. Considering that anakinra may mask signs of infection such as fever, a low threshold for further investigation will be advocated. A complete cell count will be measured at 72 hours and 14 days to exclude the unusual cases of anakinra-related neutropenia (ANC<1,000/mm³), for which suspension of active treatment will be encouraged until return to a value of ANC>1,800/mm³ (or >1,000/mm³ if patient is African-American).

Changes to treatment for side-effects or unanticipated problems will be performed without breaking the randomization code, unless deemed necessary for the treatment of the individual patient by the physician, in which case the physician will be made aware while the remainder of the team, especially the investigators performing and interpreting the tests, will be maintained blinded.

The risks of the tests performed have been described above. In order to reduce risk, the procedures will be performed by skilled practitioners in the standard clinical fashion.

Abnormal or incidental findings will be handled on a case by case basis as clinically indicated.

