- Acute respiratory failure (not due to heart failure);
- Sepsis or other serious infection requiring antibiotic therapy;
- Acute stroke.

The analysis will consider time to first event and time to each event. It will also consider event rates at 3, 6 and 12 months, in order to favor comparisons with other studies. The number of days free of hospitalization during the first 1, 3, 6 and 12 months will also be measured and compared between groups.

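### No on-treatment comparison of serious infection is prespecified for a 14-day drug; the planned 3-, 6- and 12-month windows are 85%, 92% and 96% off-drug time and dilute any on-drug effect

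*Combined protocol and SAP*

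**What the plan says.** - **Exposure.** Section 7.1 sets 14 days of study drug in all three arms. For the higher dose: "One group of patients will receive anakinra 100 mg twice daily for 14 days".
- **Expected harm.** The background section states that anakinra raises the risk of infection, mainly of the upper airways and generally mild. Section 8.1 treats infection as data specific to the treatment: "The patient will be asked about symptoms and examined for signs of infection".
- **Adjudicated event.** The list in section 9.2 includes "Sepsis or other serious infection requiring antibiotic therapy".
- **Analysis of events.** Section 9.2 first states: "The analysis will consider time to first event and time to each event". It then adds: "It will also consider event rates at 3, 6 and 12 months, in order to favor comparisons with other studies". Its only shorter window concerns a different outcome: "The number of days free of hospitalization during the first 1, 3, 6 and 12 months will also be measured and compared between groups".
- **Methods.** The statistical analysis section (numbered 12.3) names Fisher's exact test for discrete variables at a two-tailed 0.025 level. It names no survival method, no on-treatment period and no analysis of adverse events.
- **Data available.** Section 5.2 records clinical outcomes at 2 weeks as well as at the later visits. Section 7.8 schedules adverse-event assessment at 72 hours and at 14 days (± 2 days). Section 8.3.1 collects the time of onset of each adverse event.

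**The concern.** An infection caused by the drug can arise only during the 14 days of exposure or soon after. Infections in the following weeks and months are background and occur in every arm. A cumulative rate over 3, 6 or 12 months mixes the two and pulls the ratio between arms towards 1. The reason 9.2 gives for its windows is comparability with other studies, which has nothing to do with exposure to this drug.

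Section 5 states safety as an aim, and the trial tests two doses. If the long-window rates are the figures reported, infections could be called similar across arms when the on-drug risk was materially higher. A 14-day table added after unblinding would be open to the charge that the window was chosen afterwards.

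**Working it through.** The plan gives no infection rate, infection power or on-drug share, so there is no figure of its own to reproduce. The pilot infection rates are not legible in the text available and are not used.

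**Inputs from the documents:** 14 days of drug (7.1); windows of 3, 6 and 12 months (9.2), taken as T = 91.3, 182.6 and 365.25 days; 33 patients per arm (12.2), so 66 on anakinra and 33 on placebo.

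**Assumed:** an on-drug hazard ratio (HR) of 2 or 3, falling to 1 after day 14, and the background hazards below.

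**1. Off-drug share = 1 − 14/T.**
1 − 14/91.3 = 84.7%; 1 − 14/182.6 = 92.3%; 1 − 14/365.25 = 96.2%.

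**2. Observed ratio for a doubled on-drug hazard.** For rare events the ratio is 1 + f, where f is the share of control-arm infections falling in days 1-14. If the hazard in days 1-14 is m times the later hazard, f = 14m / (14m + T − 14). For example, with m = 3 at 3 months, f = 42/(42 + 77.3) = 0.35.

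| Early hazard relative to later (m) | 3 months | 6 months | 12 months |
|---|---|---|---|
| 1 (constant) | 1.15 | 1.08 | 1.04 |
| 3 | 1.35 | 1.20 | 1.11 |
| 5 | 1.48 | 1.29 | 1.17 |
| 10 | 1.64 | 1.45 | 1.28 |

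**3. Signal and noise in each window.** Take a constant hazard with 10% placebo risk at 91 days: λ = −ln(0.90)/91. Then placebo risk = 1 − exp(−λT) and anakinra risk = 1 − exp(−λ[T + (HR − 1)·14]). For HR = 3, 66 v 33:

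| Window | Placebo v anakinra | Risk ratio | Difference (SE), points |
|---|---|---|---|
| Day 14 | 1.6% v 4.7% | 2.95 | 3.1 (3.4) |
| 3 months | 10.0% v 12.9% | 1.29 | 2.9 (6.7) |
| 12 months | 34.5% v 36.6% | 1.06 | 2.1 (10.2) |

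The longer windows add no excess infections, while the standard error doubles by 3 months and triples by 12. For HR = 2 the risk ratios are 1.98 at day 14, then 1.14, 1.07 and 1.03 at 3, 6 and 12 months.

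**4. A single Cox hazard ratio.** Under the model in step 3, one hazard ratio fitted to 3, 6 or 12 months of follow-up comes to about 1.16, 1.08 and 1.05 for a true 2, and 1.32, 1.17 and 1.09 for a true 3.

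**5. What a 14-day comparison can deliver.** Under step 3 with HR = 3, the expected numbers by day 14 are 66 × 4.7% ≈ 3.1 on anakinra and 33 × 1.6% ≈ 0.5 on placebo. The chance of no placebo event is (1 − 0.016)^33 ≈ 59%, and the ratio is then undefined. For a doubling at 33 v 33 and two-sided 0.025, assumed 14-day control risks of 2%, 5%, 10% and 15% give power of about 4%, 7%, 13% and 21% (normal approximation).

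**The case against.** Four points deserve weight.

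- **The rates are not the only analysis.** A reader might infer that infection is compared only as 3-, 6- and 12-month rates. The documents do not support that: 9.2 puts time to first event and time to each event first and adds the rates. Curves by arm keep event timing and could show early separation. This stands. But no method or on-drug period is named, and a single summary hazard ratio would be diluted about as much (step 4).
- **The dilution depends on the hazard shape.** A reader might also infer that a doubled risk must show as a ratio near 1. That needs a constant background hazard, which the documents do not give. Patients have just had an acute admission with catheterisation, so early clustering is plausible and the 3-month ratio could be 1.35 to 1.64. The 10% in step 3 is likewise illustrative; it implies 34.5% on placebo at 12 months. This stands.
- **Section 8 covers harm.** It provides for infection enquiry, dated adverse events and DSMB review every 6 months with the option to unblind, and the case report form has an adverse-event review on each treatment day. On-drug infections will therefore be collected. However, neither section 8 nor 12.3 plans a comparison of them between arms.
- **A 14-day comparison is very thin.** Step 5 confirms it. The gain is an estimate matched to exposure, not a powered test. Clinical outcomes are also secondary exploratory endpoints, so neither the primary CRP analysis nor the sample size is affected.

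**Conclusion.** The concern holds as a gap in prespecification. No on-treatment comparison of serious infection is planned, and the stated rate windows are 85%, 92% and 96% off drug. The shares follow from the documents alone.

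The size of the dilution is conditional. For a doubled on-drug hazard that ends at day 14, the ratios are about 1.15, 1.08 and 1.04 under a constant background hazard. With an early hazard 3 to 10 times the later one, they are about 1.35 to 1.64 at 3 months and 1.11 to 1.28 at 12 months. Across this range the observed excess is about 15% to 64% of the true excess at 3 months and 4% to 28% at 12 months. The change is worth making because it is cheap and concerns the harm the protocol itself expects.

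**What to change.** In section 9.2, add a prespecified on-treatment comparison of serious infection and other treatment-emergent adverse events, from first dose to the day-14 visit, for anakinra against placebo and for each dose separately. Report counts and risk differences with exact confidence intervals, and state that this is the main estimate of drug-related infection risk. Keep the time-to-event analysis and the 3-, 6- and 12-month rates alongside it, and leave the heart-failure and death analyses as planned.

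The cost is a short addition to the analysis text and one further table from dated events already collected; no new visits or data are needed. The downside is sparse data: intervals will be wide and the ratio may be undefined, which is why the risk difference should lead. The text should say that absence of a difference in this window is not evidence of safety.

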9.3 Implications of the findings of the event-adjudicating committee

The events will be adjudicated only after the completion of the study, and therefore the findings by the committee will have no implications on the conduct of the study.

10) DISCONTINUATION OF TREATMENT AND WITHDRAWAL

10.1 Reasons for Discontinuation of Treatment or Withdrawal from the Study

Patients may withdraw from the study at any time. The investigators can withdraw any patient at any time from the study if medically necessary. It will be extremely important to obtain complete follow-up data on each patient, except on those who withdraw consent to release such information. It will be documented whether or not each patient completed the study. If for any reason the study treatment or observations were discontinued, the reasons will be recorded and the IRB will be informed.

Reasons for discontinuation of anakinra (or placebo):

- 1) Neutropenia (ANC<1000/mm³)*;
- 2) Systemic infection (sepsis)*;
- 3) Surgery *;
- 4) Cancer;
- 5) Hypersensitivity reaction (rash, anaphylaxis);
- 6) Severe injection site reactions *;
- 7) Need for immunosuppressant therapy;
- 8) Stroke *.

^{*} treatment may be restarted after condition resolved

10.2 Handling of Withdrawals

Loss to follow-up can occur due to patients' withdrawal or unreported death. Patients that have withdrawn from treatment will still be offered to complete all the functional assessments to analyze data in an intention-to-treat strategy. If patients are lost to follow up and their clinical condition cannot be established (alive vs dead, hospitalized vs not), they will be excluded from the initial analysis, and then reintroduced for sensitivity analysis considering all potential outcomes.

10.3 Termination of Study

The decision regarding continuation or termination of the study will be solely based on safety data. Interim analyses will be performed upon request by the DSMB. The co-Pls will meet every month (or sooner in case of unanticipated serious adverse events) to discuss enrollment, withdrawals, and adverse events. If protocol modifications are warranted, close consultation with the DSMB and the IRB will be required.

11) STATISTICAL CONSIDERATIONS

12.1 Study Hypothesis

We hypothesize that IL-1 blockade with anakinra will reduce the area-under-the-curve for CRP during the first 14 days with a greater reduction to be seen with high-dose anakinra, and that this will translate in more favorable cardiac remodeling and prevention of heart failure.

12.2 Sample Size Considerations

The sample size for this study is calculated according to the primary endpoint of difference in the AUC for CRP between anakinra (high dose) compared with anakinra (standard dose) and placebo. Given an expected average AUC for CRP of 350±250 mg/l for placebo-treated STEMI patients (based on the pilot studies) and an average AUC for CRP of 175±150 mg/l for anakinra (standard dose)(also based on the pilot studies), 33 patients per group would provide a 85% power (alpha 0.025 considering multiple groups) to detect a further 50% reduction in the anakinra (high dose)(estimated AUC for CRP of 88±75 mg/l) vs anakinra (standard dose) and a >99% power (alpha 0.025) vs placebo. A conservative estimate of 20% loss to follow-up or withdrawal would retain >80% power for all analysis.

Communication with DSMB members will be primarily through the executive secretary. It is expected that study VCU-ART3 investigators will not communicate with DSMB members about the study directly, except when making presentations or responding to questions at DSMB meetings or during conference calls.

a. DSMB Members and NHLBI Program Staff

DSMB members and their expertise are listed in Appendix A. NHLBI Program Staff involved in the study. Consistent with NHLBI policy, the DSMB is assigned an Executive Secretary (ES) to provide an unbiased staff interface for the DSMB, especially during executive sessions. The ES is responsible for assuring the accuracy and timely transmission of the final recommendations and DSMB minutes.

b. Scheduling, Timing, and Organization of Meetings

DSMB meetings will be held at the Virginia Commonwealth University, Richmond, VA, unless otherwise specified. For DSMB members residing outside of Virginia, telephone participation will be allowed for all meetings. The purpose of the first meeting is to review and discuss this Charter, to provide an overview of study VCU-ART3 activities, to review and make recommendations about the protocol(s), and to determine the frequency of interim analyses and whether data will or will not be masked to identity of randomized groups. Enrollment in a study cannot begin until the DSMB's recommendation for approval has been accepted by the Director, NHLBI, and IRB approval has been obtained at each site.

Meetings are usually held approximately twice a year, every 6 months, with additional meetings or conference calls scheduled as needed. Once the DSMB has established its working routine, consideration can be given to replacing one meeting per year with a conference call, if the agenda permits. Meetings and conference calls will be scheduled by the DCC in collaboration with the NHLBI Program Office.

- For this DSMB, meetings will be held twice per year.
- The DSMB will monitor the progress of the present trial.
- No interim efficacy analyses are planned; however an interim analysis could be performed at any time to assess efficacy and futility, if requested by the 3 or more members of the DSMB.
- The DSMB may choose to stop enrollment on the basis of safety data observed. If safety
 concerns are found, further enrollment will not be allowed until issues are resolved. If no
 safety concerns are found, enrollment will continue until the target sample size is
 reached.

The agenda for DSMB meetings and calls may be drafted by the executive secretary. The secretary will finalize the agenda after consultation with the DSMB Chair. The agenda

and meeting materials should be distributed by the DCC 4 weeks before each meeting or call.

The ES will collect and document all potential conflicts of interest from each member of the DSMB related to the design, conduct, interpretation, and publication of the study. Before each meeting, when the agenda is sent out, the ES will ask all DSMB members to state whether they have developed any new conflicts of interest since last meeting. This review will be conducted in addition to the review for conflicts of interest conducted by the VCU IRB at the time of initial IRB approval. If a new conflict is reported, the Chair and staff will determine if the conflict limits the ability of the DSMB member to participate in the discussion. The DSMB also will review adverse event data, other safety data, quality and completeness of study data, and enrollment data at each meeting to ensure proper trial conduct.

It is expected that all DSMB members will attend every meeting or call. However, it is recognized that this may not always be possible. Quorum for voting is considered to be half the number of standing members plus one. The Board may wish to decide if particular expertise is needed within the quorum for the meeting to be valid. All standing Monitoring Board members are voting members. The Board may also wish to decide in advance whether *ad hoc* members can vote.

A quorum of this DSMB is considered to be 3 members

c. Discussion of Confidential Material

DSMB meetings and calls will be organized into open, closed, and executive sessions.

- During the **open sessions**, information will be presented to the DSMB by the study investigators and NHLBI staff as appropriate, with time for discussion.
- During the closed sessions, the DSMB, DCC, and NHLBI staff will discuss confidential
 data from the study VCU-ART3, including information on efficacy and safety by
 treatment arm, if available. The DSMB will decide whether to remain masked to the
 treatment assignments at each meeting. If the closed session occurs on a conference
 call, steps will be taken to ensure that only the appropriate participants are on the call,
 and to invite others to re-join the call only at the conclusion of the closed session.

The DSMB may elect to hold an **executive session** in which only the DSMB members and NHLBI Executive Secretary are present in order to discuss study issues independently. Voting on recommendations will follow Roberts' Rules of Order (**Robert's Rules of Order Newly Revised (10th Edition) RONR** by Henry M. Robert III, William J. Evans (Editor), Daniel H. Honemann (Editor), Thomas J. Balch (Editor), Sarah Corbin Robert, Henry M. Robert III, General Henry M. Robert)

If the executive session occurs on a conference call, steps will be taken to ensure that only the appropriate participants are on the call, and to invite others to re-join the call only at the conclusion of the executive session.

At the conclusion of the closed and executive sessions, the participants will be re-convened so that the DSMB Chair can provide a summary of the DSMB's recommendations. This provides an opportunity for study investigators, the DCC, and NHLBI to ask questions to clarify the recommendations. The meeting is then adjourned.

d. Reports of DSMB Deliberations

- Formal minutes: The NHLBI ES is responsible for the accuracy and transmission of the formal DSMB minutes for the Director, NHLBI, within 14 days of each meeting or call. These minutes prepared to summarize the key points of the discussion and debate, requests for additional information, response of the investigators to previous recommendations, and the recommendations from the current meeting. Prior to submission to the Director, minutes will be reviewed by key NHLBI staff before being forwarded to the DSMB Chair for final review and approval. The DSMB Chair may sign the minutes or indicate approval electronically via email. Then, the minutes are sent to Office of the Director, NHLBI, for OD approval. Subsequently, recommendations of the Board are sent to the DCC and the primary study investigator(s); and included in the materials for the subsequent DSMB meeting to be approved by voice vote at that meeting. Once they have been voted and approved by the Board, they are considered Final.
- Reports to IRBs: Because this DSMB is convened to supervise a multi-center study, the NHLBI program office will prepare a memo documenting Board recommendations and submit it to primary study investigator(s) and DCC within 21 days of each meeting.
 Primary study investigator(s) or DCC will forward the memo to each participating research site. It is expected that all sites and the DCC will forward the memo to their IRB.
- If the DSMB does not identify any safety or other protocol-related concerns, within 30 days after a DSMB meeting, the NHLBI Program Office will prepare a Summary Report that will state that:
 - a review of outcome data, adverse events, and information relating to study performance (e.g., data timeliness, completeness, and quality) across all centers took place on a given date:
 - the observed frequency of adverse events did not exceed what was expected and indicated in the informed consent;
 - o a review of recent literature relevant to the research took place and;
 - the DSMB recommended that the study continue without modification of the protocol or informed consent.

- If concerns are identified, the report to the clinical centers will outline the concerns, the DSMB's discussion of the concerns, and the basis for any recommendations that the DSMB has made in response to the concerns.
- The DSMB report to the investigators will be forwarded to the NHLBI Program Officer, including the discussion of the concerns, and the basis for any recommendations that the DSMB has made in response to the concerns (within 7 calendar days if fatal or life-threatening unexpected, suspected serious adverse reactions; or within 14 days for unanticipated problem that is not an SAE or within 15 calendar days for all non-fatal, non-life threatening unexpected, suspected serious adverse reactions, or within 30 days of receipt of the DSMB or IRB report for all other unanticipated problems or scheduled meetings).
- The report will be distributed by the **DCC** to each clinical center. It is the responsibility of each clinical center to forward this information to the local IRB.

e. Reports to the DSMB

For each meeting, the DCC, with input from NHLBI staff, will prepare summary reports and tables to facilitate the oversight role of the DSMB. The DSMB should discuss at the first or subsequent meetings what data they wish to review and how it should be presented.

f. Statistical Monitoring Guidelines

At the first meeting, review of the protocol will include review of the statistical analysis plan. The DSMB should discuss the adequacy of that plan. The final plan, whether part of a research protocol or separate document, will be maintained as an appendix this charter. The DSMB should discuss the statistical monitoring procedures they propose to follow to guide their recommendations about termination or continuation of the trial (if applicable). These procedures could include guidelines for early termination for benefit, termination for futility, and termination for safety reasons (if applicable).

